demonstrate that serum SA concentrations remain above baseline values up to at least 19 h post-dose. The present study is designed to check for serum SA concentrations over 19 hours. Although 150 mg of aspirin is being increasingly used for prophylaxis there are no studies of the pharmacological effects of 75 mg and 150 mg aspirin in high-risk pregnancies. Further, there is no agreement on a gold standard test to assess aspirin adherence. Thus, there is a need to investigate aspirin dose dependent pharmacokinetics (PK) and pharmacodynamics (PD) further. Having completed a feasibility study involving healthy volunteers, we are ideally placed to conduct this study in a high-risk obstetric population in order to gather new valuable information regarding pharmacological (dynamics and kinetics) effects of suggested doses of aspirin.

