3 OBJECTIVES AND OUTCOME MEASURES/ENDPOINTS

3.1 PRIMARY OBJECTIVE

To compare aspirin pharmacokinetics (plasma SA concentrations) and pharmacodynamics (serum TbxB2 concentrations) in pregnant women at 11-16 weeks gestation' following the administration of a single oral dose of either 75 mg or 150 mg aspirin.

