3.3 PRIMARY ENDPOINT/OUTCOME

Area under the serum Tbx concentration versus time curve (AUC_{Tbx}) and SA plasma concentration versus time curve (AUC_{SA}).

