4 TRIAL DESIGN

Cross-over 2 x 2 design comparing PK/PD of a single oral dose of 75 mg aspirin with those of 150 mg of aspirin in pregnant women. Each of the participants will be given all the trial treatments in successive periods. The order in which the participants receive each treatment is determined at random.

The study aims to compare the plasma concentrations of SA and the pharmacological effects (by measuring serum Tbx concentration) of two doses of aspirin prescribed in clinical practice; it is not designed to compare the efficacy or safety of the medicine

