8.6 DOSAGE SCHEDULES

Study participant will be expected to take 75 mg of aspirin (1 tablet) on one occasion and 150 mg of aspirin (2 tablets) on the other. Those doses will be taken 1 week apart to account to 7 day washout period.

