10.3 STATISTICAL ANALYSIS PLAN

Descriptive statistics will be used to describe the study population, Tbx2 and SA levels. Analyte levels in the 75 mg and 150 mg group will be compared at each time point by independent t-test or by nonparametric Wilcoxon tests depending of the nature of the data obtained. The area under the curve (AUC) for all analyses over the 24 hour period will also be analyzed using analysis of variance including sequence, period, and treatment effects. IBM SPSS version 21 statistical software will be used to analyse the data.

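### The AUC model in section 10.3 lists no woman term, so fitted as written it loses the crossover's within-woman precision; a log-scale 150/75 ratio with its interval should be the main result

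*Protocol*

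**What the plan says.** Section 3.3 makes two areas under the curve primary: serum thromboxane and the "SA plasma concentration versus time curve". The objective in 3.1 is "To compare aspirin pharmacokinetics (plasma SA concentrations) and pharmacodynamics (serum TbxB2 concentrations") after the two single doses, and section 4 has each participant receive both in random order. Section 8.6 gives the doses as "75 mg of aspirin (1 tablet) on one occasion and 150 mg of aspirin (2 tablets) on the other".

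Section 10.3 has one model for the AUC of every analyte, which "will also be analyzed using analysis of variance including sequence, period, and treatment effects". It names no woman (subject) term, no scale, no ratio and no interval. The sentence before it has analyte levels "compared at each time point by independent t-test or by nonparametric Wilcoxon tests".

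Section 10.1 sizes the trial on thromboxane AUC only. It uses a population SD because no within-subject SD was available, and expects power above 80% because the within-subject SD is usually smaller.

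**The concern.** A 2 x 2 crossover earns its small sample by comparing each woman with herself. In an analysis of variance, the term for woman within sequence takes stable differences between women out of the error. The terms listed in 10.3 do not include it, and the independent t-test beside them also treats the two doses as if given to different women. If an analyst fits what is written, the intervals for both primary AUCs are too wide, and the gain that 10.1 expects from the smaller within-subject SD does not appear.

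The second issue concerns SA alone. With no ratio or interval named, the default output is a test of no treatment difference. For SA that compares one tablet with two of the same product. Equality is almost certainly false there, so a significant p-value would tell the reader very little.

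**Working it through.** **Inputs from the protocol.** 14 women, 7 per sequence (10.1); 1:1 allocation (7.3.1); both doses in each woman (4); dose ratio 150/75 = 2 (8.6); alpha 0.05 (10.1).

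**Assumptions, not in the documents.** Log-normal AUC; between-woman CV 30% or 50%; within-woman CV 15%, 25% or 35%; true 150/75 SA ratio of 1.5, 2 or 2.7.

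**1. The plan's own figure.** The only power statement is 80% for a 1 SD difference in thromboxane AUC, SD 109.7. If 109.7 is the within-subject SD, SE = 109.7 × √(2/14) = 41.5, difference/SE = √7 = 2.65, df = 12. A one-sided 5% difference test gives 80.2%, a two-sided test 68.1%, and the equivalence test that 10.1 names (margin 1 SD, true difference 0) 60.4%. No such figure exists for SA, so this does not settle the SA point. It does show that the hoped-for gain in 10.1 needs a within-woman error term.

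**2. The error term.** Write σw² and σb² for the within- and between-woman variances on the log scale.
- With woman within sequence: 12 error df, expected error mean square σw².
- As listed: 28 AUCs less 4 parameters (mean, sequence, period, treatment) leave 24 df. Twelve carry σw² + 2σb² and twelve carry σw², so the expected mean square is [12(σw² + 2σb²) + 12σw²]/24 = σw² + σb².

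In the balanced design the estimated treatment contrast is the same and its true variance is 2σw²/14. Only the reported standard error changes.

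**3. Interval width.** σ² = ln(1 + CV²): 0.0223, 0.0606 and 0.1156 for within-woman CV 15, 25 and 35%; 0.0862 and 0.2231 for between-woman CV 30 and 50%. The 95% factor is exp(t × √(2 × error variance/14)), with t = 2.179 on 12 df and 2.064 on 24 df.

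| Between CV | Within CV | With woman term | As listed |
|---|---|---|---|
| 30% | 15% | 1.13 | 1.29 |
| 30% | 25% | 1.22 | 1.35 |
| 30% | 35% | 1.32 | 1.42 |
| 50% | 15% | 1.13 | 1.47 |
| 50% | 25% | 1.22 | 1.51 |
| 50% | 35% | 1.32 | 1.57 |

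For example, the last row as listed is exp(2.064 × √(2 × 0.3387/14)) = exp(0.454) = 1.57. Simulation (20,000 trials per setting) gives median factors slightly lower: 1.13-1.31 with the woman term and 1.28-1.56 as listed. Coverage of the as-listed 95% interval is 98.6-100%. On the raw scale, rejection of equality at a true ratio of 1.5 falls from 72-100% to 33-96%.

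**4. The SA equality test, with the woman term present.** At within-woman CV 35% on the log scale, ln 2/SE = 0.693/0.1285 = 5.4. Over all settings and both scales, simulated rejection is 98-100% at a true ratio of 2. At 1.5 it is 72-100% (raw) and 82-100% (log). Significance therefore does not separate 1.5 from 2. Beyond these settings, the log-scale power at ratio 2 is 99.2% at within-woman CV 40% and 94.5% at 50%.

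**5. Reading the SA ratio against 2.** Testing the log ratio against ln 2 rejects in about 5% of trials at a true ratio of 2, and in 54-99.8% at 1.5 or 2.7. At within-woman CV 35% that power is only 54-58%. Pre-dose SA also matters. If baseline adds B to both areas and the dose adds A or 2A, the ratio is (2A + B)/(A + B), which is below 2 under exact proportionality. With B = 0.1A, purely as illustration, it is 2.1/1.1 = 1.91.

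**The case against.** The strongest defence is that 10.3 is shorthand. Lists of fixed effects often leave the subject term implicit, section 4 plainly describes a crossover, and scale, normalisation and reporting format are commonly left to a statistical analysis plan, which may exist but is not at hand. On scale and format this stands: 10.3 does not say the data are untransformed, and raw is only the default reading. On the woman term it is weaker. The protocol commits to a list of terms for its primary endpoint, next to an unpaired test of the same women.

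A reader might go further in three ways that the documents do not support.

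- **That the SA analysis is empty.** It is not. The objective is to compare SA after two doses, and the treatment contrast estimates that difference. Only the p-value is uninformative. The protocol also sets no decision rule that joins the two primary AUCs.
- **That the trial should test dose proportionality.** That aim is not stated. Section 2 says "there is a need to investigate aspirin dose dependent pharmacokinetics (PK) and pharmacodynamics (PD) further", and much of its SA argument concerns detection up to 19 hours as an adherence marker. Setting the ratio against 2 is an added reading.
- **That a raw-scale interval is wider than a log-scale one.** Put on the same footing, as half-width relative to the estimated excess over 75 mg at a true ratio of 2, the ranges are 25-53% (raw) and 24-56% (log). Raw is narrower in three of the six settings. The log scale is preferable because it gives a ratio and suits a spread that grows with the mean, not because it is always more precise.

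**Conclusion.** The point holds, and 10.3 should be changed. The main defect is the missing woman term: followed literally, the model overstates the standard error for both primary AUCs and gives up the within-woman precision that justifies a crossover of 14. The error is conservative. It costs precision and power and does not produce false positives. Its size depends on the assumed CVs and grows with the ratio of between- to within-woman variance. If the analyst adds the woman term unprompted, this loss disappears.

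The SA p-value is a lesser issue. Its near-certain significance rests on exposure rising by roughly half or more when the dose doubles, which is an assumption. The stated comparison is still estimated; it needs to be reported as a ratio with an interval.

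**What to change.** In 10.3, replace the AUC sentence by an analysis of log(AUC) with sequence, period, treatment and woman within sequence (random or fixed). Name the 150/75 geometric mean ratio with its 95% confidence interval as the main result for both SA and TbxB2.

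Optionally, as a secondary and descriptive reading, set the SA ratio beside the dose ratio of 2. State first how pre-dose SA enters the AUC, and note that precision may be too low to tell 1.5 or 2.7 from 2.

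The cost is a few lines of wording, with no new data or visits. The downside is that the result is read as a ratio rather than in concentration units; descriptive AUCs by dose can be kept beside it.

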10.4 INTERIM ANALYSIS

Due to small sample size and short duration of the trial no interim analysis is planned.

11 DATA MANAGEMENT

11.1 DATA COLLECTION TOOLS AND SOURCE DOCUMENT IDENTIFICATION

Source Data Definition

ICH E6 section 1.51, defines source data as "All information in original records and certified copies of original records or clinical findings, observations, or other activities in a clinical trial necessary for the reconstruction and evaluation of the trial. Source data are contained in source documents (original records or certified copies)."

The basic concept of source data is that it permits not only reporting and analysis but also verification at various steps in the process for the purposes of confirmation, quality control, audit or inspection. A number of attributes are considered of universal importance to source data and the records that hold those data. These include that the data and records are:

- Accurate
- Legible
- Contemporaneous
- Original
- Attributable
- Complete
- Consistent
- Enduring
- Available when needed

Source Documents

ICH E6 1.52, defines source documents as "Original documents, data and records (e.g., hospital records, clinical and office charts, laboratory notes, memoranda, participants' diaries of evaluation checklists, pharmacy dispensing records, recorded data from automated instruments, copies or transcriptions certified after verification as being accurate and complete, microfiches, photographic negatives, microfilm or magnetic media, x-rays, participant files, and records kept at the pharmacy, at the laboratories, and at medico-technical departments involved in the clinical trial)."

Case report forms (CRF)

A case report form (CRF) is a form on which individual patient data required by the trial protocol are recorded. CRF will be printed and used at the bedside to complete at each study visit. Only the data required by the protocol will be captured in the CRF.

Following the visit data to be transferred to the study specific database.

SHORT TITLE: DORA

EudraCT number: 2021-000071-36

CRF forms are a source document and therefore will be filed in participants notes.

11.2 DATA HANDLING, RECORD KEEPING AND ACCESS TO DATA

Participant identifiable information will be handled in line with GDPR 2018 principles, will be stored on the Newcastle upon Tyne Hospitals NHS Foundation Trust's secure server under the Caldicott approval.

All participants will be given unique identifier to allow anonymization of the data and samples. Anonymized electronic research data will be transferred to Newcastle University secure server for analysis. No personal identifying information will be presented/published in the study outputs.

The research team and local R&D monitors may require access to the participant's clinical notes; participants will be informed of this in the participant information sheet, and permission to do so form part of the consent form.

11.4 Archiving

After the end of the study, data will be stored securely at a restricted access secure storage facility used by the Newcastle Hospitals NHS Foundation Trust. Research data generated by the study will be stored for 5 years.

SHORT TITLE: DORA

EudraCT number: 2021-00071-36

12 MONITORING, AUDIT & INSPECTION

The trial will follow the Monitoring plan agreed with Sponsor.

13 ETHICAL AND REGULATORY CONSIDERATIONS

13.1 ETHICAL CONSIDERATIONS

Before the start of the trial, approval will be sought from a REC for the trial protocol, informed consent forms, and invitation letters.

All substantial amendments that require review by REC will not be implemented until the REC grants a favourable opinion for the trial (note that amendments may also need to be reviewed and accepted by the MHRA and the sponsor).

All correspondence with the REC will be retained in the Trial Master File/Investigator Site File

An annual progress report (APR) will be submitted to the REC within 30 days of the anniversary date on which the favourable opinion was given, and at the end of the trial (we expect this study to be completed in less than 12 months therefore no annual report will be submitted). It is the Chief Investigator's responsibility to produce reports as required and to notify the REC of the end of the trial.

In case of premature end of the trial, the Chief Investigator will notify the REC, including the reasons for the premature termination

Within one year after the end of the trial, the Chief Investigator will submit a final report with the results, including any publications/abstracts, to the REC.

All recruitment will be conducted by an experienced member of the research team. Full, written consent will be obtained by a delegated member of the research team following eligibility assessment by a GCP trained obstetrician. At all stages, potential participants will be reminded that they are under no obligation to take part and that their decision will have no impact on any future care they may receive. It will be ensured that participants have the capacity to give consent, have a full understanding of the purpose of the research, the involvement required and the risks and benefits involved.

Every effort will be made to minimise potential discomfort or distress. There is a possibility that participants will experience some discomfort from the venipunctures at the time of cannulation, however, they will be offered the option of a local anesthetic, and the researcher is experienced in undertaking venipuncture. It is not anticipated that any unusual discomfort will be experienced. Neither patients nor clinicians will be given the TbxB₂ or SA results.

The study will be performed in time for patients to commence their planned prophylactic therapy in full i.e., participants will be seen by a research team as soon as feasible to allow treatment to be

SHORT TITLE: DORA

recommenced not later than 16 weeks of gestation, therefore the washout period will not affect outcomes of preventative treatment.

13.2 REIMBURSEMENT

To reimburse participants for their time, at the time of the protocol completion, participants will be given an appointment to attend a 4D growth scan at 28 weeks gestation in Newcastle upon Tyne Hospitals NHS Foundation Trust (retail price approx. £90.00). Growth scan will be performed using local scan and reporting procedures.

Participants travel expenses will be reimbursed via the Trust process of claiming travel expenses, alternatively Taxis can be arranged by the Trust's Transport Team.

13.3 PUBLIC AND PATIENT INVOLVEMENT

Members of the public were involved in review of a scope (lay summary), design and incentives for this trial. High risk women viewed this research important to them and despite high demands on time would have expressed interest in participation considering trial would provide participants with a letter to the employer to justify absence from work.

Sampling time point are arranged to avoid busy time periods such as school drop offs and pick-ups.

Women also preferred to have a 4D scan rather than monetary reimbursement as though that a scan could be of a higher emotional value.

13.4 REGULATORY COMPLIANCE

The trial will not commence until a Clinical Trial Authorisation (CTA) is obtained from the MHRA and Favourable REC opinion.

The protocol and trial conduct will comply with the Medicines for Human Use (Clinical Trials) Regulations 2004 and any relevant amendments

Before any site can enroll patients into the study, the Chief Investigator/Principal Investigator or designee will ensure that appropriate approvals are in place. Specific arrangements on how to gain approval from participating organisations are in place and comply with the relevant guidance. Different arrangements for NHS and non NHS sites are described as relevant.

For any amendment to the study, the Chief Investigator or designee, in agreement with the sponsor will submit information to the appropriate body in order for them to issue approval for the amendment. The Chief Investigator or designee will work with sites (R&D departments at NHS sites as well as the study delivery team) so they can put the necessary arrangements in place to implement the amendment to confirm their support for the study as amended.

SHORT TITLE: DORA

13.5 PROTOCOL COMPLIANCE

It is the responsibility of the CI to ensure that the clinical trial is run in accordance with GCP and the protocol. This task may be delegated to a suitably qualified or experienced member of the research team but the CI will retain overall responsibility.

Protocol deviations, non-compliances or breaches are departures from the approved protocol.

Deviations from the protocol and GCP occur in clinical trials and the majority of these events are technical deviations that are not serious breaches. These events should be documented on the deviation tracking log (this will be provided as part of the ISF). The trial manager will ask sites to provide the research team of their deviation tracking log at intervals throughout the study and before any monitoring visits. If no deviations have been identified during a particular interval, sites are required to send an email to the trial manager to confirm this.

If the deviation constitutes a violation, the site must complete a protocol violation form (again a blank template will be provided to the site as part of the ISF) and send a copy of this completed form to the Trial Manager within 3 working days. The violation must also be entered on to the deviation tracking log.

Deviations or violations that are found to frequently recur are not acceptable and could be classified as a serious breach.

13.6 NOTIFICATION OF SERIOUS BREACHES TO GCP AND/OR THE PROTOCOL

A serious breach is a breach which is likely to effect to a significant degree:

the safety or physical or mental integrity of the subjects of the trial; or

the scientific value of the trial

The sponsor must be notified immediately of any incident that may be classified as a serious breach. The sponsor will notify the MHRA and the NHS REC within the required timelines in accordance with the Sponsor SOP.

13.7 DATA PROTECTION AND PATIENT CONFIDENTIALITY

All identifiable data will be handled in line with GDPR 2018 and Caldicott principles.

Patient identifiable information will be accessed for screening purposes by a clinical research team using the Trust's policies and procedures for access of the data.

Once participants enrolled in the study, a unique identifier will be given to enable to store research samples and data to minimize access to identifiable information.

EudraCT number: 2021-000071-36

SHORT TITLE: DORA

Participants' consent forms will be stored securely in the locked metal cabinet within secure research facility in the Trust.

Only clinical research team will be able to access identifiable information for safety assessment, clinical purposes and to monitor the trial.

Data generated by the trial will be stored for the duration of the data clearance and transferred in anonymised form to Newcastle University for statistical analysis.

13.8 FINANCIAL AND OTHER COMPETING INTERESTS FOR THE CHIEF INVESTIGATOR, PIs AT EACH SITE AND COMMITTEE MEMBERS FOR THE OVERALL TRIAL MANAGEMENT

Authors of the protocol declare no conflict of interest.

Funding

Costs related to the study will be supported by the Newcastle upon Tyne Hospitals NHS Charity

Some R&D system serum Thromboxane assays will be provided by Bio-Techne corporation.

The Newcastle upon Tyne Hospitals Foundation Trust Clinical Research Facility will be supporting the trial with provision of their facilities.

13.9 INDEMNITY

The Sponsor will provide indemnity in the event that trial participants suffer negligent harm due to the management of the trial. This indemnity will be provided under the NHS indemnity arrangements for clinical negligence claims in the NHS.

The substantial employers of the protocol authors will provide indemnity in the event that trial participants suffer negligent harm due to the design of the trial.

The study sites will provide indemnity in the event that trial participants suffer negligent harm due to the conduct of the trial at their site under the NHS indemnity arrangements for clinical negligence claims in the NHS. NHS Organisations must ensure that site staff without substantive NHS contracts hold honorary contracts to ensure they can access patients and are covered under the NHS indemnity arrangements. Study staff without NHS contracts e.g., General Practitioners or Dentists will provide their own professional indemnity.

This is a non-commercial study and there are no arrangements for non-negligent compensation.

SHORT TITLE: DORA

EudraCT number: 2021-000071-36

